g. Samples to be taken C5, C7, C10 and C13 only. After C13 a sample will be obtained every 6 months (± 1 month) for up to 3 years.

h. Sample to be taken during Safety Run-in only.

i. Only in case of full infusion of GEN3009 on Day 1

j. Only in case of GEN3009 split dose between Day 1 and Day 2

Table 14 Visit Assessment Schedule for MRD – Expansion GEN3009 + GEN3013

Cycle	Cycles 1, 2, 3, 5, 7, and 10	Cycle 13 and onward
Day or Time post dose (window)	Day 1 (+2 days)	Day 1 (+2 days)
Whole blood MRD ^a	X	A whole blood sample will be obtained every 6 months (± 1 month) for up to 3 years
Bone marrow aspirate MRD	
For B-cell NHL subjects with bone marrow involvement at baseline: If a subject is in CR by FDG-PET, a portion of the aspirate collected to confirm CR will be used to assess MRD.For B-cell NHL subjects with no bone marrow involvement at baseline, no bone marrow examination for MRD is required.If a subject is MRD-positive in the bone marrow but maintains CR, an additional bone marrow aspirate will be collected after 3 months, if clinically feasible.	

a. Upon reaching CR on PET-CT scan, an additional blood sample will be collected if not within 2 weeks of another collection to evaluate MRD.

Table 15 GEN3013 Repriming Cycle – Expansion GEN3009 + GEN3013 (including Safety Run-in)

	Day 1	Day 8	Day 15	Day 22
Body Weight	X		X	
Complete physical examination	X			
Lymph node examination	X			
Neurological Evaluation (ICANS) ^b	X	X	X	X
Vital signs ^c	X	X	X	X
12-Lead ECG (triplicate)	X			
ECOG Performance Status	X			
Constitutional Symptoms (ie, B Symptoms)	X		X	
Adverse Events	X	X	X	X
Previous and concomitant medications	X	X	X	X
Concomitant procedures	X	X	X	X
STUDY TREATMENT ADMINISTRATION				
Hospitalization ^d			X	
Premedications ^e	X	X	X	X
CRS prophylaxis ^f	X	X	X	X
GEN3013 administration	X	X	X	X
LOCAL LABORATORY ASSESSMENTS				
Hematology	X		X	
Biochemistry	X		X	
Coagulation	X		X	
Immunoglobulins (IgA, IgE, IgG, gM)	X			
Urinalysis	X			
Pregnancy Test (urine or serum) ^g	X			
TLS Monitoring			X	
CENTRAL LABORATORY ASSESSMENTS				
Immunophenotyping (by flow cytometry)	X ^h	X ^h	X ^h	X
Pharmacokinetics (GEN3009 and GEN3013)	X ^h	X ^{h,i}	X ^{h,i}	X ^{h,i}
Anti-drug antibodies	X ^h			

- a. Once the full repriming cycle is completed, the subject should resume treatment with Day 1 of the next planned cycle (subsequent to the cycle during which the dosing was delayed); see Section 7.4.2.2.

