- b. ICANS evaluation, based on (Lee et al., 2019), must also be performed in the presence of CRS-type symptoms or any neurological signs/symptoms.
- c. Vital sign assessment must be conducted before dosing and 1 hr (± 30 min) following each dose

- d. Subjects are to be hospitalized for at least 24 hours after the third (full dose) administration of GEN3013 in a repriming cycle. Additional or longer hospitalization should be per the investigator's discretion.
- e. Premedication should be administered 30 min to 2 hours before administration of GEN3013.
- f. CRS prophylaxis consists of prednisolone 100 mg (or alternative steroid equivalent) daily for Days 1-4, 8-11, 15-18, and 22-25 of a repriming cycle. On GEN3013 dosing days, corticosteroid should be given 30 min to 2 hrs prior to GEN3013 injection. See also Section [6.2.2](#).
- g. Results must be available before dosing.
- h. Predose only.
- i. PK sample for GEN3009 only if dosed weekly.

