CRS symptoms (not limited to chills, fever, hypotension, and hypoxia)	
• The first dose of GEN3013 is a priming dose (ie, a lower dose than subsequent doses); the second dose is an intermediate dose (ie, higher than the priming dose but lower than the subsequent full-dose levels) (Section 6.4.2).• Premedication is mandatory prior to the first 4 administrations of GEN3013 and optional for later administrations (Section 6.2.2).

	
• Prophylactic corticosteroids are mandatory for 2 days following each of the first 4 weekly administrations of GEN3013; for subsequent administrations, prophylactic steroids are only necessary if CRS \geqGrade 2 occurs following the fourth GEN3013 administration (Section 6.2.2).• Hospitalization for CRS monitoring is mandatory for at least 24 hours following the third dose (first full dose) of GEN3013 administration only. A lead-in dose of GEN3009 will be given a week before GEN3009 + GEN3013 combination to reduce the potential risk of CRS with GEN3013. 
See Section 7.5.2 and Appendix 13 for supportive care and management of CRS.

ICANS	Monitoring of the neurologic and cognitive status (including, but not limited to, confusion, expressive aphasia, headache, seizures and altered level of consciousness) of subjects to secure timely introduction of supportive care (Sections 7.5.3 and 9.3.1.1 and Appendix 14)
Clinical TLS	Laboratory monitoring; prophylaxis and management guidelines (Appendix 4).

The risks to subjects treated with the GEN3009 and GEN3013 combination will be minimized by a preceding safety run-in phase to inform the tolerability of the combination treatment before opening the Expansion phase, staggered dosing among subjects within a DL, requirement for hospitalization following the third dose (first full dose) of GEN3013 treatment, and established guidelines for the recognition and management of CRS and ICANS in addition to the compliance with the eligibility criteria, trial procedures, and close monitoring and management of TEAEs.

Furthermore, aggregate safety data will be reviewed by an independent data monitoring committee (DMC) on a regular basis to ensure the benefit to risk ratio remain acceptable for trial subjects.

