6.2.2 Premedication and CRS Prophylaxis in GEN3009 + GEN3013 Combination Cohort

Premedication (ie, corticosteroids, antihistamines, antipyretics and a leukotriene receptor antagonist) and post-infusion corticosteroids are mandatory for GEN3009 and GEN3009 + GEN3013 doses in Cycle 1 and Cycle 2 Day 1 as described in [Table 23](#). In subsequent treatment (ie., Cycle 2 Day 8 and beyond), steroid may be optional. Refer to [Appendix 3](#) for corticosteroid equivalent. The leukotriene receptor antagonist only needs to be given in Cycle 1. Premedication with antipyretics and antihistamines should be administered at all cycles.

If there is a Grade 3 IRR during Cycle 1, corticosteroid is required for Cycle 2 but may be at a reduced dose ie, prednisolone at 80 mg IV. The use of corticosteroid is optional for subsequent cycles.

If CRS \geq Grade 2 occurs following the fourth dose of epcoritamab administration (Cycle 2 Day 1 dose), premedication with corticosteroid and 3-day consecutive corticosteroid administration is recommended to continue for the rest of GEN3013 doses in Cycle 2. From Cycle 3 and onward, corticosteroid may be optional for premedication with antipyretics and antihistamines should be administered at all cycles.

Table 23 Premedication and Post-infusion Medication for GEN3009 + GEN3013 Combination

		Corticosteroids	Antihistamines	Antipyretics	Leukotriene receptor antagonist	
Cycle 1	Premedication for GEN3009	Day 1 (Predose)*	Prednisolone 100 mg IV (or equivalent)	Diphenhydramine 50 mg IV or oral (PO) or equivalent)	Acetaminophen 650 to 1000 mg PO (or equivalent)	Montelukast, 10 mg PO
	Premedication for GEN3009 + GEN3013 (priming dose at 0.16 mg)	Day 08 (Predose)*	Prednisolone 100 mg IV (or equivalent)	Diphenhydramine 50 mg IV or PO (or equivalent)	Acetaminophen 650 to 1000 mg PO (or equivalent)	Montelukast, 10 mg PO
		Day 09	Prednisolone 100 mg IV or PO (or equivalent)			
		Day 10	Prednisolone 100 mg IV or PO (or equivalent)			
	Premedication for GEN3009 + GEN3013 (intermediate dose at 0.8 mg)	Day 15 (Predose)*	Prednisolone 100 mg IV (or equivalent)	Diphenhydramine 50 mg IV or PO (or equivalent)	Acetaminophen 650 to 1000 mg PO (or equivalent)	Montelukast, 10 mg PO
		Day 16	Prednisolone 100 mg IV or PO (or equivalent)			
		Day 17	Prednisolone 100 mg IV or PO (or equivalent)			

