	Premedication for GEN3009 + GEN3013 administration 48 mg)	Day 22 (Predose)*	Prednisolone 100 mg IV (or equivalent including oral dose)	Diphenhydramine 50 mg IV or PO (or equivalent)	Acetaminophen 650 to 1000 mg PO (or equivalent)	Montelukast, 10 mg PO

		Corticosteroids	Antihistamines	Antipyretics	Leukotriene receptor antagonist
		Day 23	Prednisolone 100 mg IV or PO (or equivalent)		
		Day 24	Prednisolone 100 mg IV (or equivalent including oral dose)		
Cycle 2	Premedication for GEN3009 + 4th GEN3013 administration (48 mg)	Day 1 (Predose)*	Prednisolone 100 mg IV (or equivalent)	Diphenhydramine 50 mg IV or PO (or equivalent)	Acetaminophen 650 to 1000 mg PO (or equivalent)
		Day 2	Prednisolone 100 mg IV or PO (or equivalent)		
		Day 3	Prednisolone 100 mg IV or PO (or equivalent)		
		Day 8 and beyond	If CRS \geq Grade 2 occurs following the 4th dose of epcoritamab administration (Cycle 2 Day 1 dose), premedication with corticosteroid and 3-day consecutive corticosteroid administration is recommended to continue for the rest of GEN3013 doses in Cycle 2. From Cycle 3 and onward, corticosteroid may be optional.		

* Premedication should be given 30 minutes - 1 hour prior to the trial treatment. On the days when both trial drugs are given, administer GEN3013 s.c. first, monitor the subject for 30 minutes to 1 hour, then start the GEN3009 infusion. GEN3013 will be administered prior to GEN3009.

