7.4.2.2 GEN3013 Dose Modification Rules

Dose reduction is not allowed for GEN3013 on an individual subject level in this trial. Refer to Section [4.3](#) for dosing rationale.

If a dose is delayed more than 6 weeks, the subject should be asked to perform an unscheduled visit for collection of AEs, concomitant medications, laboratory values (including hematology, biochemistry, and coagulation values), and a limited physical examination (as clinically indicated) after consultation with the sponsor's medical monitor.

A repriming cycle is necessary if dose is delayed at certain time points, as described below. A repriming cycle consists of a weekly schedule of a priming dose, intermediate dose, and 2 full doses. Refer to [Table 15](#) for the repriming cycle Visit Assessment Schedule.

A repriming cycle should occur:

- For the second GEN3013 full dose onward (ie, C2D1), if the interval between the previous dose of GEN3013 and next planned dose exceeds 6 weeks.

During the repriming cycle, CRS prophylaxis must be resumed with 3 consecutive days of corticosteroids beginning at each GEN3013 dose, until at least 1 full dose of GEN3013 is administered without subsequent occurrence of CRS Grade ≥ 2 (see Section [6.2.2](#)).

Once the full repriming cycle is completed, the subject should resume treatment with Day 1 of the next planned cycle (subsequent to the cycle during which the dosing was delayed). For example, if the subject experiences a 7-week delay after C3D1, the subject should receive a repriming cycle, then continue treatment at C4D1. GEN3009 dose will continue as scheduled.

If GEN3013 dose is delayed, withheld, or discontinued during the combination treatment period, GEN3009 can be continued if approved by the sponsor's medical monitor.

Refer to Section [7.4.3](#) for information about dose modifications due to AEs.

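### Table 15 footnote f prescribes four steroid days with each GEN3013 repriming dose; Section 7.4.2.2 prescribes three for the same cycle

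*Protocol*

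**What the plan says.** Two places in the protocol set the corticosteroid course for a repriming cycle.

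- **Table 15, footnote f** (Section 1, Visit Assessment Schedules): prednisolone 100 mg or equivalent, "daily for Days 1-4, 8-11, 15-18, and 22-25 of a repriming cycle". It adds: "On GEN3013 dosing days, corticosteroid should be given 30 min to 2 hrs prior to GEN3013 injection". The table marks CRS prophylaxis on Days 1, 8, 15 and 22.
- **Section 7.4.2.2** (GEN3013 Dose Modification Rules): "CRS prophylaxis must be resumed with 3 consecutive days of corticosteroids beginning at each GEN3013 dose". This continues until at least one full dose has been given without CRS of Grade 2 or higher afterwards. The section also defines the cycle: "A repriming cycle consists of a weekly schedule of a priming dose, intermediate dose, and 2 full doses".

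The two places point to each other. Section 7.4.2.2 sends the reader to Table 15 for the repriming schedule, and footnote a of Table 15 sends the reader back to Section 7.4.2.2. Both also cite Section 6.2.2, which does not mention repriming.

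The remaining steroid text concerns ordinary dosing:

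- **Table 16** (Section 2.3.2): "Prophylactic corticosteroids are mandatory for 2 days following each of the first 4 weekly administrations of GEN3013".
- **Table 23** (Section 6.2.2): steroid on Cycle 1 Days 8-10, 15-17 and 22-24 and on Cycle 2 Days 1-3, that is, the dosing day plus two.
- **Section 6.2.2, text**: if CRS of Grade 2 or higher follows the fourth dose, premedication with corticosteroid and "3-day consecutive corticosteroid administration is recommended to continue for the rest of GEN3013 doses in Cycle 2".

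**The concern.** Both rules are current text and both name the repriming cycle, yet they give different numbers of steroid days per dose. A site that follows the cross-references meets both and is not told which to use. CRS is named in Section 2.3.2 as one of the main risks of GEN3013, and this is the prescribed prophylaxis against it. Sites could therefore give different steroid courses to subjects in the same situation, and one of the two courses is not what the clinical team meant. What is at stake is the treatment subjects receive and consistency between sites.

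**Working it through.** **Inputs**

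- Doses in a repriming cycle: four, weekly (one priming, one intermediate, two full), on Days 1, 8, 15 and 22 (Section 7.4.2.2; Table 15).
- Steroid days per dose in Table 15: from the day ranges in footnote f.
- Steroid days per dose in Section 7.4.2.2: 3, counted from the dose.
- Daily steroid dose: 100 mg prednisolone, from footnote f and Table 23. Section 7.4.2.2 states no dose, so using 100 mg for its totals is an assumption.

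Neither place states a total, so there is no planned figure to reproduce.

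**Table 15.** Inclusive days = last day - first day + 1.

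- 4 - 1 + 1 = 4; 11 - 8 + 1 = 4; 18 - 15 + 1 = 4; 25 - 22 + 1 = 4.
- Total: 4 x 4 = 16 days; 16 x 100 mg = 1600 mg.

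**Section 7.4.2.2.** The total depends on when prophylaxis stops.

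| Case | Steroid days | Total | Prednisolone | Excess in Table 15 |
|---|---|---|---|---|
| All four doses covered, as Table 15 marks | 1-3, 8-10, 15-17, 22-24 | 4 x 3 = 12 | 1200 mg | 16 - 12 = 4 days (Days 4, 11, 18, 25); 400 mg; 4/12 = 33% |
| Stops after a Day 15 full dose without CRS Grade 2 or higher | 1-3, 8-10, 15-17 | 3 x 3 = 9 | 900 mg | 16 - 9 = 7 days (Days 4, 11, 18 and 22-25); 700 mg; 7/9 = 78% |

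**Can the two texts be reconciled?**

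1. *A dosing-day premedication plus three further days.* No. Footnote f gives the steroid before the injection on dosing days, and its ranges start on those days. Section 7.4.2.2 also starts its three days at the dose. Both counts include the dosing day.
2. *Three days as a floor.* The wording does not say so. The sentence in Section 7.4.2.2 sets a minimum for the number of full doses, not for the number of steroid days.
3. *Section 6.2.2 as arbiter.* It does not address repriming. Table 23 there, and Table 16, cover the first four GEN3013 doses (Cycle 1 Days 8, 15 and 22; Cycle 2 Day 1). Both amount to the dosing day plus two, so they support 3 days by analogy. The conditional sentence in the text of Section 6.2.2 is weaker support. It concerns later Cycle 2 doses, applies only after CRS of Grade 2 or higher, is a recommendation, and names premedication separately from the three-day course.

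Footnote f is therefore the only place with explicit four-day blocks.

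**The case against.** The strongest reply is that little turns on this. A subject given steroids on Days 1-4 has also had the three consecutive days that Section 7.4.2.2 requires, so no dose goes without prophylaxis under either text. The rule applies only to combination-cohort subjects whose GEN3013 interval exceeds 6 weeks, from the second full dose onward, which is after the 28-day DLT period. All of that stands, and it keeps the point minor. It does not remove the conflict, because the number of 100 mg steroid days still depends on which page the site reads.

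A second reply is that the size is not a single number. That also stands: 33% holds only if all four doses are covered, so the range is given above.

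Two stronger readings are tempting, and the documents support neither.

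- *Table 15 over-treats.* A reader might infer this because the other steroid schedules point to three days. But those schedules are not written for repriming, and no text says that three days was meant here. If four days is intended, Section 7.4.2.2 is the faulty text and gives one day too few per dose.
- *Table 15 also contradicts Section 7.4.2.2 by marking Day 22 unconditionally.* A reader might see a second error there. The stopping condition in Section 7.4.2.2 is a minimum, so prophylaxis with the second full dose is compatible with it.

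**Conclusion.** The inconsistency is real and confined to the number of steroid days per repriming dose: four in Table 15 footnote f, three in Section 7.4.2.2. Table 15 gives 4 to 7 more steroid days per repriming cycle (400 to 700 mg), assuming 100 mg a day under both rules and no further delay within the cycle. The lower figure applies if all four doses are covered, the upper if prophylaxis stops after an uncomplicated Day 15 full dose. The documents give no repriming rate, so no trial-wide total can be computed. The balance of the text favours three days, but which count was intended is for the clinical team to confirm. No endpoint, analysis set or DLT decision is affected, and the point is one to consider rather than a threat to the trial.

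**What to change.** Change the day ranges in footnote f of Table 15 to Days 1-3, 8-10, 15-17 and 22-24, in line with Section 7.4.2.2 and Table 23. Leave the Day 22 mark in the table as it is. If the clinical team intends four days, leave footnote f and change the count in Section 7.4.2.2 to four instead.

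The edit is to one footnote or one phrase, with no change to the Table 15 grid, visits, data collection or analysis. Because it alters a prescribed steroid course, it may not count as a purely administrative change under Section 14.1, which otherwise requires a formal amendment with ethics committee approval. It should therefore go in with the next protocol amendment.

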2 INTRODUCTION

2.1 Background

2.1.1 Overview of Disease

Non-Hodgkin lymphomas (NHLs) comprise a heterogeneous group of lymphoid malignancies that originate from B-cell lymphocytes, T-cell lymphocytes, and natural killer (NK) cells. In the US, an estimated 74,200 new cases of NHL will be diagnosed in 2019 with 19,970 deaths expected ([SEER, 2019](#)). Approximately 85-90% of NHLs are derived from B cells (B-cell NHL). According to the World Health Organization 2016 classification of lymphoid neoplasm ([Swerdlow et al., 2016](#)), B-cell NHL subtypes including diffuse large B cell lymphoma (DLBCL), high-grade B-cell lymphoma (HGBCL), mantle cell lymphoma (MCL), primary mediastinal large B-cell lymphoma (PMBCL), follicular lymphoma (FL), marginal zone lymphoma (MZL), chronic lymphocytic leukemia/small lymphocytic lymphoma (CLL/SLL), etc, are categorized as mature B-cell neoplasms.

2.1.1.1 Therapy for DLBCL

DLBCL is the most common aggressive lymphoma representing 30-35% of all NHL cases ([Ghielmini et al., 2013](#)). Although the majority of DLBCL patients can be cured with combinational immuno-chemotherapy (ie, rituximab plus doxorubicin-based combination chemotherapy, R-CHOP), approximately one-third of patients will develop relapsed or refractory (R/R) disease. It is known DLBCL patients with high-risk features (eg, double-hit lymphoma, transformed lymphomas, or early relapse) will become refractory to standard therapies and will have limited alternatives for cure.

For patients with R/R DLBCL, approximately 60% remain sensitive to conventional second-line immunochemotherapy; and these patients can undergo subsequent high-dose chemotherapy (HDT) followed by autologous hematopoietic stem cell transplantation (HSCT) and achieve long-term survival ([Gisselbrecht et al., 2010](#); [Sehn et al., 2012](#)). On the contrary, R/R DLBCL patients who do not respond to second-line immunochemotherapy only have a life expectancy of 3 to 4 months ([Elstrom et al., 2010](#); [Friedberg, 2011](#)). Due to advanced age and/or comorbidities only half of R/R DLBCL patients are eligible for HDT-HSCT. For transplant-eligible candidates who have failed second-line therapy or whose disease has relapsed post-transplantation, the prognosis is dismal. Recently, CD19-directed chimeric antigen receptor (CAR) T cell therapies (ie, KYMRIAH®, YESCARTA®) have revolutionized the treatment of refractory B-cell lymphoid malignancies and demonstrated durable remissions in R/R large B-cell lymphomas including DLBCL, HGBCL, and PMBCL ([Locke et al., 2019](#); [Schuster et al., 2019](#)). However, potentially life-threatening toxicities including cytokine release syndrome (CRS) and neurotoxicity, extended production time precluding patients with rapidly progressing disease, and high-treatment expense have limited the access. Taken together, most patients with R/R DLBCL cannot expect to be cured with secondary therapies and a new investigational therapy with manageable toxicities is needed.

2.1.1.2 Therapy for FL

FL is the most common subtype of indolent NHL and accounts for 22-25% of all new diagnoses. Although indolent in nature and often responding to the initial treatment, FL of advanced stage is

incurable with frequent relapses. In advanced, symptomatic FL, first-line treatment is anti-CD20 monoclonal antibodies (ie, rituximab or obinutuzumab) in combination with multi-agent chemotherapy. HSCT is typically reserved for patients with relapsed disease (Cheson et al., 2014; NCCN, 2019). Although the current treatments are initially effective in inducing responses in most patients, they are not curative and show decreasing efficacy with increasing lines of therapy.

In relapsed FL, treatment in patients with late relapse (>2 years; 80%) is reinduction by salvage treatment with rituximab-containing chemotherapy followed by rituximab maintenance therapy for 2 years. Irrespective of first-line treatment choice, early relapse occurs in 20% within 24 months and is a robust predictor of poorer overall survival (OS), with only 34-50% of patients being alive at 5 years. Second-line treatments include lenalidomide with rituximab (Andorsky et al., 2016; Leonard et al., 2019), polatuzumab vedotin with rituximab (Morschhauser et al., 2019), idelalisib for double-refractory cases (Gopal et al., 2014a; Gopal et al., 2017), and allogeneic HSCT in selected fit patients. Finally, bispecific antibodies targeting CD3 and CD20 may represent an attractive treatment as preliminary data have shown high response rates in R/R FL with acceptable toxicity profiles (Dickinson et al., 2019; Topp et al., 2019). In summary, early relapsed FL represents a particular unmet medical need; treatment options are limited for patients who have failed several lines of therapy.

2.1.1.3 Therapy for CLL

CLL is the most common leukemia in adults in Western countries, accounting for approximately 25% to 30% of all leukemias in the US with estimated 20,720 new cases and 3,930 deaths (Siegel et al., 2019). Worldwide, there are approximately 105,000 cases per year, of which 35,000 are deaths (Global Burden of Disease Cancer et al., 2018).

Most patients with newly diagnosed CLL present with asymptomatic disease and can be monitored without therapy until disease progression. For symptomatic or high-risk disease, standard of care includes cytotoxic chemotherapy (fludarabine, cyclophosphamide, bendamustine, and chlorambucil) in combination with anti-CD20 monoclonal antibodies (ie, rituximab or obinutuzumab) (Hallek et al., 2010); (Goede et al., 2014). Although bendamustine plus rituximab (BR) had shorter median progression-free survival (PFS) as compared to fludarabine, cyclophosphamide, plus rituximab (FCR) (Eichhorst et al., 2016), BR regimen can be an alternative first-line treatment for physically fit older patients (>65 years) due to decreased toxicity. Recently, kinase inhibitors ibrutinib and idelalisib have gained considerable momentum as first-line treatment for high-risk CLL with TP53 aberrations (O'Brien et al., 2016; Sharman et al., 2014). Ibrutinib demonstrated improved objective response rate (ORR) (86% vs 35%), 2-year PFS (89% vs. 34%) and 2-year OS (98% vs. 85%) as compared to chlorambucil (Burger et al., 2015). Subsequently, 2 large Phase 3 studies comparing ibrutinib alone or with rituximab to BR (older patients ≥ 65 years) or FCR (younger patients < 65 years) in the front-line setting were conducted. Although both studies showed the ibrutinib rituximab combination was superior to BR and FCR with longer PFS, a notable lack in the ability of ibrutinib to induce complete response (CR) and minimal residual disease (MRD)-negative remissions were observed: 30% CR, with MRD-negative in 59% on FCR and 8% on BR; whereas ibrutinib-containing regimens on these trials, the CR rates were <20% with <10% of patients achieved MRD negativity in the peripheral blood (Woyach et al., 2018). Most recently, in an international Phase 3 CLL14 study, the combination of venetoclax and obinutuzumab was compared to chlorambucil and obinutuzumab in patients with untreated CLL with medical comorbidities; a superior 2-year PFS rate of 88% over 64% was observed (Fischer et al., 2019).

In R/R CLL, a Phase 3 study comparing the combination of venetoclax and rituximab to BR has shown very encouraging activity: 2-year PFS 85% vs. 36% with BR. This PFS improvement was observed across all high-risk groups including patients with del(17p) karyotype. There was also an impressive ORR of 92% with 84% achieving MRD-negative status in the peripheral blood (Seymour et al., 2018). Preliminary data from a Phase 1 study showed the doublet of venetoclax and obinutuzumab appeared to be highly effective in R/R CLL irrespective of cytogenetic risk factors with an overall best response rate of 95% (CR/CRi, 37%) (Flinn et al., 2019). Overall, in CLL, a new agent that can potentially induce deeper remission with higher percentage of MRD negativity is warranted for further investigations.

